COVER PAGE

Title: Feasibility Study for Treating Trichotillomania With Wearable Device and

App System

NCT04241120

Document Date: 7/18/2019

STUDY PROTOCOL AND STATISTICAL ANALYSIS PLAN

STUDY PROTOCOL

Potential participants completed a phone screening with an independent evaluator (IE) to determine preliminary study eligibility (Figure 1). Those deemed likely eligible provided consent and were invited to complete a baseline evaluation via video conference, during which the IE administered the MINI, TDI, and NIMH-TSS. The participants also completed the MGH-HS and MIST-A online. Eligible participants were randomly assigned (via block randomization with a 2:1 ratio) to one of the following two conditions: 1) prototype wrist-worn motion detection device and accompanying app (n=10; Figure 2) or 2) reminder bracelet (n=5). Unequal sample sizes were obtained due to the exploratory nature of the comparison, and because the primary focus of the pilot trial was to test the usability, acceptability, and feasibility of device and app, rather than compare the device and app combination to the reminder bracelet. All participants were informed they would receive either a wrist-worn device and accompanying phone app or a stand-alone wrist-worn device. They were told that the two devices would be compared to assist researchers with the continued product development. The IE was masked to treatment assignment.

After randomization, participants were exposed to either the device and app or the reminder bracelet for 4 weeks. A short, four-week intervention period was chosen because past studies that evaluated AEDs led to near-zero levels of hair pulling (Rapp et al., 1998) and finger sucking (Ellingson et al., 2000; Stricker et al., 2001; Stricker et al., 2003) almost immediately. At midpoint (2 weeks) and post (4 weeks), participants were reevaluated via videoconference by the IE. At each visit, the IE administered the NIMH-TSS to the participants via a video call. Participants were instructed not to discuss their treatment assignment with the IE. After completing the video call, participants were sent a link to a Qualtrics survey that included the MGH-HS, MIST-A, and a self-report questionnaire. The IE did not have access to the Qualtrics survey until the study was completed.

Device + App Condition

During the 4-week trial, participants wore the device and interacted with the app. The first module of the app provided participants with psychoeducation about hair pulling and HRT (Figure 3). The second module addressed awareness training, during which participants were instructed to choose one hair pulling site that would be called their "danger zone." They created a detailed description of their hair pulling in the danger zone. Next, participants wore the device for three days, during which they were told to notice the real-time reminders (i.e., vibration) that could occur when they pulled from their danger zone.

After wearing the device for three days, the app informed the participants that they could "test" their awareness. During the awareness testing phase, the device would still detect the trained behavior, but the vibration was delayed by approximately seven seconds. During the delay, the participants could "beat" the device by pushing a button on the device before it vibrated. Pushing the button before the device vibrated was used to demonstrate awareness of the hair pulling. Upon demonstrating 80% awareness for any three of the previous five days, participants received competing response training (CRT) via the app.

Using written explanations and video demonstrations, patients were taught to do a competing response when they noticed they were pulling or about to pull their hair. For their competing response, participants were instructed to gently make a fist with their

primary hair pulling hand, hold it against their chest, and discreetly wiggle the device back and forth with their other hand for approximately three seconds. This allowed the device to automatically record when the competing response was being performed. Participants were then instructed to keep holding their fist against their chest until the urge to pull passed. The device was able to detect competing response use and calculate how often competing responses were done versus how often they pulled their hair. If participants used their competing response for 80% of their pulling episodes from their trained danger zone for any three of the previous five days, they were sent daily pop-up motivational support messages such as "believe you can, and you will" and "breathe and take this one day at a time" via the mobile app.

Reminder Bracelet Condition

Participants in the reminder bracelet group received a bracelet that was physically identical to the prototype awareness device in the device and app condition. However, there was no accompanying app and no motion detection ability. Rather than vibrating when hair pulling was detected, the reminder bracelet was pre-programmed to vibrate twelve times per hour at random intervals. This was based on past internal observational data of the average number of times those with hair pulling pulled per hour during the development of the motion recognition algorithm of the device. Participants were told the device would vibrate randomly several times per hour as a reminder not to hair pull. The device was to be worn during all waking hours for four weeks.

STATISTICAL ANALYSIS PLAN

For the usability, acceptability, feasibility, and perceived efficacy, participants completed a 21-question survey and rate each of the areas on a scale of 1 (strongly disagree) to 5 (strongly agree). Mean scores were compiled and examined. To examine the impact of the device and app on hair pulling severity, Wilcoxon signed-rank tests were conducted on pre-post NIMH-TSS and MGH-HS total scores. To examine the preliminary comparison between the device/app system and reminder bracelet, a 2 (group) by 3 (time) mixed analysis of variance (ANOVA) was conducted to determine whether there were significantly greater decreases in the NIMH-TSS and MGH-HS total scores from baseline to post-treatment among participants who were given the device and app relative to the reminder bracelet.

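### Low severity, cheap to improve: the bracelet vibrates 12 times an hour in all waking hours, and nothing exempts the masked evaluator's video calls

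*Combined protocol and SAP*

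**What the plan says.** All references are to the combined protocol and SAP.

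- **Study Protocol, masking.** "The IE was masked to treatment assignment". Participants were asked not to talk about their assignment with the IE, and the IE could not see the online survey until the study had ended.
- **Study Protocol, assessments.** "At midpoint (2 weeks) and post (4 weeks), participants were reevaluated via videoconference by the IE". The scale that the IE scores live on these calls is named in the next sentence: "At each visit, the IE administered the NIMH-TSS to the participants via a video call". The MGH-HS and MIST-A were self-reported online.
- **Reminder Bracelet Condition.** Participants had "a bracelet that was physically identical to the prototype awareness device in the device and app condition". It had no motion detection; instead "the reminder bracelet was pre-programmed to vibrate twelve times per hour at random intervals". The rate rests on "past internal observational data of the average number of times those with hair pulling pulled per hour", gathered while the motion algorithm was being developed. On wear: "The device was to be worn during all waking hours for four weeks".
- **Device + App Condition.** The unit vibrates when it detects pulling from the chosen danger zone. In the awareness-testing phase the vibration is held back about seven seconds and the wearer can press a button first. After competing response training, the wearer holds a fist to the chest and wiggles the unit with the other hand.
- **Statistical Analysis Plan.** "To examine the preliminary comparison between the device/app system and reminder bracelet", a 2 by 3 mixed ANOVA is applied to the NIMH-TSS and MGH-HS totals.

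No section says whether the unit is worn, silenced or removed during an IE call.

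**The concern.** The three stated measures deal with speech, data access and appearance. None deals with behaviour on camera, and there the two arms differ by design. The bracelet vibrates whatever the wearer is doing. The device-arm unit vibrates on detected pulling, and its wearers may press a button or wiggle the unit.

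As the units are described, a vibration with no pulling would point to the bracelet, and a button press or device wiggle would point to the device arm. An IE who noticed such a cue and knew how each unit works could form a view of the assignment while scoring.

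What is at stake is narrow. The NIMH-TSS is the only severity outcome with a masked rater, and its week-2 and week-4 ratings enter the comparison between arms. The baseline rating precedes randomisation and is untouched. The usability survey and the self-reported MGH-HS do not depend on IE masking.

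**Working it through.** **What can be reproduced.** The 12 per hour rate cannot be rederived, because the internal data behind it are not given. The allocation agrees with its ratio: 15 × 2/3 = 10 and 15 × 1/3 = 5.

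**Inputs from the documents.** Bracelet rate 12 per hour at random (Reminder Bracelet Condition); wear in all waking hours for four weeks (same section); two IE calls per participant after randomisation, at weeks 2 and 4 (Study Protocol); 5 bracelet participants.

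**Assumptions.** Call length T is not stated, so 5 to 30 minutes is shown. The bracelet is taken to be worn on the call.

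**Formulas.** Expected vibrations in a call are λ = 12 × T/60. Two readings of random intervals are used:

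- Poisson timing: P(at least one) = 1 − exp(−λ).
- Exactly 12 placed uniformly in each hour: P(at least one) = 1 − (1 − T/60)^12.

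| T (min) | λ | Poisson | Exactly 12 per hour |
|---|---|---|---|
| 5 | 1 | 63% | 65% |
| 10 | 2 | 86% | 89% |
| 20 | 4 | 98% | 99% |
| 30 | 6 | 99.75% | 99.98% |

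For example, at 10 minutes 1 − exp(−2) = 0.865, and at 20 minutes 1 − exp(−4) = 0.982. Among the 5 bracelet participants at week 2, the expected number with at least one vibration on the call is 5 × 0.865 = 4.3 (10 minutes) or 5 × 0.982 = 4.9 (20 minutes).

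**What the figures cover.** They give the chance that a vibration occurs. Going from there to unmasking needs three more steps: the IE notices it, relates it to what the wearer is or is not doing, and knows how each unit works. The documents are silent on all three, so no probability of unmasking can be computed.

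**Which calls.** Week 2 falls inside the wear period. Week 4 falls at its end, and the text does not say whether the call came before or after wear stopped. The bracelet calls at issue are therefore 5 (week 2 only) or up to 10 (both).

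**Device arm.** No vibration rate on a call can be given. The unit responds to detected pulling from one site, and how often that happens in front of a camera is not stated.

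**The case against.** The strongest reply is that this argues from silence. The text is a short summary in the past tense, without the IE's instructions or a call script. It states that the IE was masked, and nothing in it contradicts that. Vibration is described only as a reminder to the wearer; no section says that it can be heard or seen over video. The trial's main focus is usability, acceptability and feasibility, not the comparison. By the text's own tense, an instruction may come too late.

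Much of this stands. It confines the point to a possible route to unmasking that the stated measures leave open, and it keeps the severity low. It does not close the route: wear in all waking hours includes the week-2 call unless someone says otherwise.

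Two stronger readings are tempting and unsupported:

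- From 86% to 98%, a reader might infer that masking probably failed. The figures count vibrations, and the documents give nothing on how many would be noticed. Any noticing rate would be a guess and would bound nothing.
- Because the 12 per hour came from observed pulling, a reader might infer that both arms vibrate equally often on a call, so that only the link to pulling could separate them. That figure is an average pulling rate from algorithm development. It is not a vibration rate for the device arm, least of all during an interview. The two rates could be similar or far apart.

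**Conclusion.** The point holds as a low-severity gap with a cheap remedy. As written, the bracelet is active in all waking hours, the masked IE rates the NIMH-TSS on live video at least once inside that period, and no stated measure covers the unit or the wearer on camera. If the bracelet is worn, at least one vibration is likely for any assumed call of 10 minutes or more (86% upwards) and more likely than not at 5 minutes (63%).

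The conclusion rests on the bracelet being worn on the call and on the assumed call lengths. It does not show that the IE was unmasked, and the direction of any bias is unknown. The exposure is limited to the NIMH-TSS at weeks 2 and 4. The comparison it feeds is described as exploratory and preliminary, with 10 against 5 participants, so it should be treated as an improvement to consider and not as a defect that undermines the trial.

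**What to change.** Add one line to the participant and IE instructions, the same in both arms: the wrist unit is off and out of camera and microphone range during each IE call after randomisation, and wear then resumes. The statement about wear in all waking hours should note this exception so that the two agree. This removes the vibration, button-press and device-wiggle cues. It does not remove the fist-to-chest gesture, which trained device-arm participants may still make.

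The cost is the wear lost on at most two calls. At 10 to 30 minutes each that is 20 to 60 minutes. If 16 waking hours a day is assumed, four weeks of wear is 16 × 28 = 448 hours, and the loss is 0.333/448 = 0.07% to 1/448 = 0.22%. The wear in all waking hours behind this total is stated only for the bracelet arm; the device-arm section gives no daily schedule. No analysis changes.

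If the calls are already complete, as the past tense suggests, report whether units were worn on them, including whether the week-4 call came before wear ended. If they were worn, state this as a masking limitation of the NIMH-TSS comparison. That takes one or two sentences.

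### Do the usability survey means need a stated visit, arm and number of responders before they can be used?

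*Combined protocol and SAP*

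**What the plan says.** The Study Protocol section explains the unequal arms (10 device and app, 5 reminder bracelet) by saying that the "primary focus of the pilot trial was to test the usability, acceptability, and feasibility of device and app", and not the comparison between arms. On this aim the Statistical Analysis Plan has two sentences. The first begins "For the usability, acceptability, feasibility, and perceived efficacy, participants completed a 21-question survey" and describes five-point agreement ratings. The second is "Mean scores were compiled and examined".

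On timing, the Study Protocol section says: "At midpoint (2 weeks) and post (4 weeks), participants were reevaluated via videoconference by the IE". Later in the same paragraph: "After completing the video call, participants were sent a link to a Qualtrics survey that included the MGH-HS, MIST-A, and a self-report questionnaire". Nothing says whether that questionnaire is the 21-question survey.

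The Device + App Condition section releases content in steps. Awareness testing comes first: "After wearing the device for three days, the app informed the participants that they could" try it. Then: "Upon demonstrating 80% awareness for any three of the previous five days, participants received competing response training (CRT) via the app". Motivational messages follow once the competing response is used "for 80% of their pulling episodes from their trained danger zone for any three of the previous five days". No latest date or automatic release is given for either later step. The Reminder Bracelet Condition section says that arm had no app.

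**The concern.** The survey carries the main aim, yet its analysis is specified less closely than the secondary ones. In the same SAP paragraph the Wilcoxon tests are pre-post and concern the device and app, and the ANOVA names two groups and three times. The survey means name neither a group nor a time.

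The visit could matter because of the staged release. A user rating the system at week 2 may not yet have met the competing response training, while the same user at week 4 may have had about three weeks of it. If the survey went out at both visits, an undated mean could be week 2, week 4 or a blend, and a reader could not tell which product had been rated. With 10 users each answer is a tenth of the mean, so a few missing answers would also count. At stake is how the trial's main descriptive result is read.

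**Working it through.** There is no stated figure to reproduce: the documents give no survey score, standard deviation, power or precision. The one internal check is that the arm sizes agree with 2:1 allocation: 15 × 2/3 = 10 and 15 × 1/3 = 5. They do.

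**1. How far can app content differ between visits?**

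Inputs, from the Device + App Condition section: 3 days of wear before awareness testing, then 3 qualifying days within a five-day window for each of two steps. Visits are taken as day 14 and day 28, counting from first wear on day 1. The higher day in each pair below assumes that a full five-day window must pass.

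| Content | Earliest unlock (after day) | Most days by day 14 | Most days by day 28 |
|---|---|---|---|
| Competing response training | 3 + 3 = 6, or 3 + 5 = 8 | 14 − 6 = 8, or 14 − 8 = 6 | 28 − 6 = 22, or 28 − 8 = 20 |
| Motivational messages | 6 + 3 = 9, or 8 + 5 = 13 | 14 − 9 = 5, or 14 − 13 = 1 | 28 − 9 = 19, or 28 − 13 = 15 |

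These are best-case limits, not observed exposure. A fast user could have seen every component by week 2, though for fewer days. A slow user might lack the training at week 2 and have it at week 4. A user who never meets the 80% rule has none at either visit. So content may differ between visits but need not, and part of the variation is between users, which naming a visit would not remove.

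**2. What could that do to a mean?**

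All rating differences and non-response counts here are assumptions.

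- A 1-point difference in k of 10 ratings shifts the device-arm mean by k × 1/10: 0.1, 0.3 or 0.5 for k = 1, 3 or 5.
- Averaging the two visits moves the mean from its week-4 value by half of any visit difference: 0.5/2 = 0.25, or 1.0/2 = 0.50.
- With k of 10 not answering, the full-arm mean on a 1-to-5 scale is undetermined over a width of k × (5 − 1)/10: 0.4, 0.8 or 1.2 for k = 1, 2 or 3.
- Pooling the 5 bracelet users would shift the mean by 5/15 of any arm difference: 0.17, 0.33 or 0.50 for differences of 0.5, 1.0 or 1.5.

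For scale, the 95% half-width of a mean of 10 is t(0.975, 9) × SD/√10, or 0.36, 0.72 or 1.07 for an assumed SD of 0.5, 1.0 or 1.5. The estimate is loose whichever visit is used.

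**3. What does the text already settle?**

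- *Arm.* The aim concerns the device and app, and bracelet users had no app to rate. The usability, acceptability and feasibility means can only sensibly be device-arm means, so the pooling shift in step 2 is not a realistic outcome.
- *Responders.* The denominator at randomisation is given (10). How many answered becomes known when the data are in, and is reported beside the mean. Figure 1 is not shown, so any counts in it could not be checked.
- *Visit.* The survey is described as completed, in the singular, and includes perceived efficacy, which is most naturally rated once the four weeks are over. This reading is likely, not certain.

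**The case for a change.** The strongest case for a change is that the visit cannot be deduced from the text. The paragraph with the Qualtrics link covers both follow-up visits, so a fair reading is that the link went out twice. The 21-question survey is never tied to the questionnaire in that link. Even a user who unlocked everything early would have had only days of competing response training to judge at week 2, against about three weeks at week 4. A clarification would take two or three sentences and no new data.

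The facts in this case stand: the visit is unstated and the two instruments are not linked. The consequence does not follow. No inference, threshold or decision depends on these means, so nothing the plan sets out to conclude changes with the visit. Release by performance is part of the intervention, and ratings of the system as each user met it are a legitimate usability measure at either visit. If both visits were surveyed, an analyst would ordinarily tabulate them separately with their counts. Counting how many users had reached the competing response training by each visit would be a useful extra, but the stated aim does not require it, and the documents do not say whether app records were kept for that purpose.

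**Conclusion.** No change to the plan follows. The SAP does leave the survey's visit unstated and does not say whether the survey is the questionnaire in the Qualtrics link. This is missing detail of a kind that analysts fill sensibly: device-arm ratings, labelled by visit, with the number who answered. The arm follows from the aim, and the number of responders is a result.

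The possible difference in exposure is real as an upper limit (at most 6 to 8 days of competing response training by week 2, at most 20 to 22 by week 4). Its effect on the means is unknown. The shifts of 0.1 to 0.5 points rest wholly on assumed rating differences, and no bias, lost rating or wrong result is shown. The conclusion assumes that the survey means stay descriptive, as the SAP has them. If a pass mark or a go/no-go decision were tied to them, the visit would have to be fixed.

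### Pre-post Wilcoxon tests with no comparator are said to examine the impact of the device and app, but they can show only within-arm change

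*Combined protocol and SAP*

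**What the plan says.** The severity analysis has two parts, in consecutive sentences of the Statistical Analysis Plan.

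- **Uncontrolled part.** "To examine the impact of the device and app on hair pulling severity, Wilcoxon signed-rank tests were conducted" on the pre-post totals of the NIMH-TSS and MGH-HS. The sentence does not say which participants are included.
- **Randomised part.** For the device/app against the reminder bracelet, "a 2 (group) by 3 (time) mixed analysis of variance (ANOVA) was conducted to determine whether there were significantly greater decreases" on the same two totals. This comparison is called preliminary.

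The Study Protocol section gives the context. Allocation was 2:1, with 10 participants on the device and app and 5 on the bracelet. It explains that "Unequal sample sizes were obtained due to the exploratory nature of the comparison", and that "the primary focus of the pilot trial was to test the usability, acceptability, and feasibility of device and app".

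On what participants knew, it says "All participants were informed they would receive either a wrist-worn device and accompanying phone app or a stand-alone wrist-worn device". In the bracelet arm "there was no accompanying app and no motion detection ability", and "Participants were told the device would vibrate randomly several times per hour as a reminder not to hair pull". The evaluator was masked to assignment.

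**The concern.** Impact is a causal word, and the plan attaches it to the test that cannot support it. A signed-rank test on paired scores asks whether scores moved between baseline and week 4. Any movement mixes a device effect with natural fluctuation, repeated assessment and expectancy. Nothing in the documents limits the result to within-arm change.

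The one analysis with a concurrent randomised control is presented as a comparison of two products. Calling it preliminary is fair at 10 versus 5; the fault lies only in the causal label on the uncontrolled test.

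The risk is a split result: the Wilcoxon test is significant, the between-arm test is not, and the report, following the plan's wording, credits the device with an improvement it did not cause.

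**Working it through.** **Inputs from the documents.** Device arm n=10, bracelet arm n=5, assessments at baseline, 2 and 4 weeks, and the two tests named above. The documents give no alpha, SD, expected change or power calculation, so there is no figure of the plan's own to reproduce.

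**Assumptions.** Two-sided alpha 0.05, normal scores, no ties, no dropout, equal SD at each visit, and no device-specific effect. Non-specific improvement is k SD of the change score. The values of k are illustrative.

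**1. Signed-rank test, n=10.** The 5% critical region is T ≤ 8. Its exact size is 2 × 25/1024 = 0.0488; T ≤ 9 would give 0.0645. Simulated rejection rates:

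| k (SD of change) | 0 | 0.2 | 0.3 | 0.5 | 0.8 | 1.0 |
|---|---|---|---|---|---|---|
| Significant | 4.8% | 8.5% | 13.1% | 28.2% | 59.6% | 78.4% |

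**2. Between-arm test, equal non-specific change.** The drift cancels. A 10-versus-5 t-test of change rejects in 5.0% of trials and the 2 x 3 group-by-time F test in about 5%, whatever k is. The split result (Wilcoxon significant, between-arm test not) therefore occurs in at least 28 − 5 = 23% of trials at k = 0.5, and at least 60 − 5 = 55% at k = 0.8.

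**3. Between-arm test, unequal non-specific change.** Participants could tell which condition they had, and only one arm had the app, so equality is not assured. Suppose non-specific change is larger in the device arm by δ SD of change. For the t-test, the noncentrality is δ/√(1/10 + 1/5) = δ/0.548 on 13 df. For the F test (2 and 26 df), take a correlation of 0.5 between all visits.

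| δ | 0.3 | 0.5 | 0.8 |
|---|---|---|---|
| t-test of change | 8.0% | 13.5% | 27.3% |
| 2 x 3 test, half the change by week 2 | 7.1% | 11.0% | 21.7% |
| 2 x 3 test, all the change by week 2 | 8% | 13% | 28% |

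The randomised contrast is better protected than the pre-post test, but not immune.

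**4. Precision (95% CI half-widths).**

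- Within-arm change: t(9)/√10 = 2.262/3.162 = 0.72 SD of change.
- Between-arm difference in change, unadjusted: t(13) × √0.3 = 2.160 × 0.548 = 1.18 SD of change.
- The same on the scale of the week-4 score: 1.18 × √(2(1 − r)) = 1.40, 1.18 and 0.92 SD for a baseline to week-4 correlation r of 0.3, 0.5 and 0.7.
- Baseline-adjusted week-4 difference: t(12) × √(0.3 × (1 − r²)), with t(12) = 2.179, = 1.14, 1.03 and 0.85 SD of the week-4 score. Allowing for chance baseline imbalance, the simulated means are 1.16, 1.06 and 0.87.

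**5. Power of the randomised contrast.** The t-test of change has about 27% power for a true difference of 0.8 SD of change, and needs about 1.66 SD for 80%. A non-significant between-arm result is therefore likely even when the device has a moderate effect, which makes the split result a practical prospect.

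**The case against.** The strongest reply is that this is a matter of wording which the next sentence largely repairs. The controlled analysis is planned on the same scales, the trial's stated focus lies elsewhere, and no alpha, success rule or decision hangs on the Wilcoxon p-value. That limits the consequence. It does not remove the fault: the causal label stays on the uncontrolled test, and a split result would be read through it.

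A second reply is that every drift size is assumed, and nothing in the documents makes 0.8 SD likelier than 0.2 SD, where the rejection rate is only 8.5%. That is right, and the figures are illustrations. Likewise, the small advantage of the 2 x 3 test over the t-test under unequal drift depends on half the change coming by week 2; it disappears if all of it comes by then.

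A third reply is that the trial had safeguards. The evaluator was masked and could not see the survey until the study ended, participants were told not to discuss assignment, the bracelet looked identical to the device, and the comparison was framed neutrally as product development. These support the randomised contrast, particularly on the evaluator-administered NIMH-TSS. They do not blind participants to whether they have an app, and they do not help a within-arm pre-post test.

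Finally, the baseline-adjusted model could be called a reviewer's preference, since renaming the Wilcoxon result cures the stated fault. The model goes further than the wording, but for a reason: once effect statements rest on 15 people, an estimate that uses the baseline score already collected gives a narrower interval than the unadjusted change contrast.

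**Conclusion.** The concern holds. As worded, the plan can credit the device and app with non-specific improvement. With no device-specific effect, the n=10 signed-rank test would be significant in about 13, 28 or 60% of trials for a non-specific improvement of 0.3, 0.5 or 0.8 SD of change, against about 5% for a between-arm test if that improvement is equal in both arms. If it is larger in the device arm by the same amounts, the between-arm t-test rejects in about 8, 14 or 27%.

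These figures rest on an assumed alpha of 0.05, normal change scores and assumed drift; the conclusion that a one-arm pre-post test cannot isolate a device effect does not. The point should be corrected, but its weight is modest in a feasibility pilot that also plans and reports the randomised comparison.

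**What to change.** - State that the Wilcoxon tests use the device arm (n=10), and describe their result as within-arm change rather than impact.
- Base any statement about the effect of the device on the randomised comparison, reported as the baseline-adjusted week-4 difference between arms with its 95% CI, and keep it exploratory.
- Describe that contrast as device/app against an active reminder bracelet, not against no treatment. Note that participants knew whether they had the app, so unequal expectancy can remain in the difference; report the evaluator masking and the neutral framing beside this.

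The cost is revised SAP wording and one small model on data already collected. The severity result becomes less precise and possibly less favourable: a 95% CI half-width of about 1.03 SD of the week-4 score at r = 0.5, against 0.72 SD for within-arm change (at r = 0.5 the SD of change equals the SD of the score, so the two are on the same scale).

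### The SAP has no rule for missing week-2 or week-4 severity scores, and the mixed ANOVA and Wilcoxon test it names are complete-case in their standard form

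*Combined protocol and SAP*

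**What the plan says.** The whole statistical plan is one paragraph, under the heading STATISTICAL ANALYSIS PLAN. It names two methods for hair-pulling severity:

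- For the effect of the device and app: "Wilcoxon signed-rank tests were conducted on pre-post NIMH-TSS and MGH-HS total scores".
- For the preliminary comparison of the arms: "a 2 (group) by 3 (time) mixed analysis of variance (ANOVA) was conducted". The question it is meant to answer is if severity on both scales falls more in the device arm than in the bracelet arm between baseline and week 4.

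The STUDY PROTOCOL section sets the visits. After baseline, "At midpoint (2 weeks) and post (4 weeks), participants were reevaluated via videoconference by the IE". The NIMH-TSS is given by the evaluator on the call. The MGH-HS is collected separately: "After completing the video call, participants were sent a link to a Qualtrics survey that included the MGH-HS, MIST-A, and a self-report questionnaire". An MGH-HS score can therefore be missing when the NIMH-TSS is present.

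The arms are 10 and 5. The documents give no analysis set, missing-score rule, imputation, sensitivity analysis, alpha, or expected or observed dropout. They also do not state that the analysis is complete-case.

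**The concern.** A classical mixed ANOVA over three visits needs all three scores from each participant. The question put to it is about change from baseline to week 4, yet a participant with both of those scores is lost if week 2 was missed. A participant who leaves after week 2 drops out of both tests, and the week-2 score already collected is not used.

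The arms are so small that each deletion counts: one person is 10% of the device arm and 20% of the bracelet arm. If those who leave are the ones doing badly, the remaining device participants look improved on average even when the device does nothing. If such loss is heavier in one arm, the comparison between arms is biased too.

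**Working it through.** **Inputs from the documents.** Device arm 10, bracelet arm 5, allocated 2:1 (STUDY PROTOCOL); 15 × 2/3 = 10 and 15 × 1/3 = 5, which agrees. Three visits: baseline, week 2, week 4. There is no power or dropout figure to reproduce.

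**Assumptions.** Normal scores with SD 1 at every visit, no true change, two-sided 5% tests. Dropout and correlations are varied because none are given.

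**1. Who the named methods keep.**

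| Scores present | Mixed ANOVA | Pre-post Wilcoxon (device arm) |
|---|---|---|
| All three | kept | kept |
| Baseline and week 4, no week 2 | dropped | kept |
| Baseline and week 2, no week 4 | dropped | dropped |

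**2. How many could be lost.** If each follow-up visit is missed independently with probability q, the ANOVA drops 15 × [1 − (1 − q)²] participants on average, of whom 15 × q × (1 − q) have a week-4 score.

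- q = 0.05: 15 × 0.0975 = 1.5 dropped; 15 × 0.05 × 0.95 = 0.7 with week 4.
- q = 0.15: 15 × 0.2775 = 4.2 dropped; 15 × 0.15 × 0.85 = 1.9 with week 4.

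**3. Bias in the device-arm completer mean.** Let the k participants of 10 with the worst week-2 change leave before week 4. Write r for the correlation of baseline with each follow-up and s for that of week 2 with week 4. Each change score has variance 2(1 − r), and the covariance of the two changes is s − 2r + 1. The completer bias is

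−[(s − 2r + 1) / √(2(1 − r))] × (sum of the k largest expected normal order statistics of 10) / (10 − k).

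The three largest order statistics are 1.539, 1.001 and 0.656, so the last factor is 1.539/9 = 0.171, 2.540/8 = 0.318 and 3.196/7 = 0.457 for k = 1, 2, 3.

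- r = 0.5, s = 0.85: multiplier 0.85/1 = 0.85; bias −0.15, −0.27, −0.39 SD.
- r = s = 0.5: multiplier 0.5/1 = 0.50; bias −0.09, −0.16, −0.23 SD.
- r = s = 0.7: multiplier 0.3/0.775 = 0.39; bias −0.07, −0.12, −0.18 SD.

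**4. False significant decrease on the device-arm Wilcoxon test**, by simulation:

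| Who leaves | 1 | 2 | 3 |
|---|---|---|---|
| At random | 2-3% | 2-3% | 2-3% |
| Worst week-2 change, correlations all 0.5 or all 0.7 | about 3% | about 5% | about 8% |
| Worst week-2 change, correlations 0.5 and 0.85 | 5-6% | 11% | 20% |
| Worst week-4 change (upper range), correlations all 0.5 or all 0.7 | 7-8% | 17% | 30-31% |

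With nobody lost, the rate is about 2.5%.

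**5. Comparison between arms.** If only the device arm loses its 1, 2 or 3 worst week-4 changers, the ANOVA interaction is falsely significant in 6-7%, 9% and 12% of trials, against 5% with no loss.

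**6. What a model on all available scores recovers.** Under the week-2 leaving rule with correlations 0.5 and 0.85, for 1, 2 and 3 leavers:

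- Completers only: bias −0.15, −0.27, −0.39 SD.
- REML model with compound symmetry: about −0.07, −0.11, −0.15 SD.
- Likelihood estimate with unrestricted covariance: about 0.00 in all three cases. This is expected, because leaving then depends only on scores the model sees.

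If leaving depends on the unseen week-4 change, the unrestricted estimate is biased too: about −0.07, −0.12, −0.18 SD at these correlations, and −0.12, −0.24, −0.36 SD with all correlations at 0.5. Each is smaller than the completer bias under the same rule (−0.17, −0.32, −0.46 SD, the step-3 factors with multiplier 1).

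**The case against.** The strongest reply is that the plan is silent rather than wrong. A reader might infer that the trial analysed completers only. The documents do not say so: it follows from the names of the methods, and carry-forward or imputation before testing is not excluded. That stands, and it is why the point is a missing rule together with a poor default. An unstated imputation step would itself need to be specified.

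A reader might also infer that a missed week 2 removes someone from both severity tests. It does not, since the Wilcoxon test uses only baseline and week 4.

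No attrition is reported. If all 15 participants gave every score, nothing changes, and random loss produces no bias. The scenarios in which poor responders leave are assumptions, and the 20% figure needs one particular correlation pattern; with equal correlations it is about 8%.

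The protocol also says that "the primary focus of the pilot trial was to test the usability, acceptability, and feasibility of device and app", and it calls the arm comparison exploratory. Missing severity scores do not touch the usability survey means. This limits the consequence. The severity tests are nevertheless the only inferential results in the plan, and the remedy is cheap.

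**Conclusion.** The concern holds as a conditional one. The SAP has no rule for missing week-2 or week-4 scores, and its named methods, run in the usual way, analyse complete cases. For the ANOVA this discards participants who have both scores that its question needs.

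The size rests on outcome-related loss, which the documents neither report nor rule out. With no true change and the 1, 2 or 3 worst week-2 changers of 10 leaving, the false-decrease rate on the Wilcoxon test runs from about 3%, 5% and 8% to 5-6%, 11% and 20%, depending on the correlations, against about 2.5% with no loss.

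It would go too far to say that the trial's severity result is a false improvement, or that the randomised comparison has been broken. The first needs outcome-related dropout. The second also needs that dropout to differ between arms. The documents show neither. Because severity is secondary to usability and feasibility, this is a change that should be made, not one on which the trial's main aim depends.

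**What to change.** - Replace the mixed ANOVA with a linear mixed model for repeated measures, fitted by REML with small-sample degrees of freedom, using every available score from all randomised participants. State a simple covariance structure in advance.
- Report the week-4 group contrast from this model, and the device-arm baseline-to-week-4 change from it beside the Wilcoxon test.
- Add one sensitivity analysis that gives leavers no change from baseline.
- Report the numbers randomised and analysed at each visit, separately for NIMH-TSS and MGH-HS because they are collected by different routes.

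The cost is SAP wording and a few lines of code. The model reduces the bias but does not guarantee its removal. Too simple a covariance leaves some (the compound-symmetry figures in the working), and leaving driven by unseen week-4 status leaves some under any structure. An unrestricted covariance costs precision: at correlations 0.5 and 0.85 the SE of the device-arm change is about 0.35 against 0.34 SD for completers with 2 leavers, and 0.39 against 0.35 with 3. The cost is higher at lower correlations (0.38 against 0.35 with 2 leavers when all are 0.5). With no missing scores the results are essentially unchanged.
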